### **9.2.8 Ordering and Accountability of Study Materials**

The MyDay Sphere and MyDay Energys lenses will either be provided by the sponsor or sourced locally by the site, whichever makes logistical sense at the time. The sites are responsible for completing accountability logs for all lenses received, dispensed and returned.

## **9.3 Visit Schedule and Procedures**

---

This study has 6 scheduled study visits (including the screening and exit visit), which are conducted on 3 visit days (Table ). The total time commitment for scheduled visits is expected to be up to 4 hours.

**Table 2: Summary of visits**

Visit code	Visit schedule	Visit Description	Duration (hrs)
1		Screening to determine eligibility and to establish optimum power of MyDay Sphere	1 (1.5 if fitting both lenses)
2*		Dispense MyDay Sphere**	0.5
3	≥7 days after V1	Review MyDay Sphere and baseline data collection	0.5
4		Fit and Dispense MyDay Energys***	0.5
5	7-10 days after V2	Review MyDay Energys	1
6		Study exit****	

\*Note: Visit 2 is only necessary if a change in MyDay Sphere lens power is required, or if a fit with MyDay Sphere is required for adaptation

\*\*Note: Visit 2 can be concurrent to Visit 1

\*\*\*Note: Visit 4 is concurrent to Visit 3

[figure not shown]
\*\*\*\*Note: Visit 6 can be concurrent to Visit 5

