## 4 Study Design

---

This is a prospective, multi-center, open label, bilateral wear, one week dispensing study comparing the clinical performance of the MyDay Sphere lenses following a refit with MyDay Energys lenses.

Habitual wearers of MyDay Sphere lenses will be reviewed at Visit 1 to ensure optimal visual acuity is being achieved. If the visual acuity and power of the habitual MyDay Sphere lens is optimal, the participant will continue to wear MyDay Sphere in the same prescription for at least 7 days after which baseline variables will be collected. If an amendment of the power of the habitual MyDay Sphere is required, participants will be dispensed with the new power of the MyDay Sphere lenses to be worn for at least 7 days. In the instance where the participant habitually wears lenses which are not MyDay Sphere, the participant will be fit and dispensed MyDay Sphere lenses to be worn for at least 7 days.

After wearing MyDay Sphere lenses for at least 7 days in the study, all participant will return for baseline variables to be evaluated and will be then be dispensed with MyDay Energys. The participant will be asked to return for evaluation after 7-10days of lens wear. Participants will exit the study following the final evaluation of MyDay Energys.

This study will be open label. Over labeling of the blister packs is not required.

[figure not shown]

Figure 1 Study flow chart.

[figure not shown]

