### **9.1 Participants**

---

Up to 120 subjects may be screened for this study. All potential subjects will be habitual wearers of MyDay Sphere or will be adapted to this lens for at least one week as part of the study. Each subject will be required to attend up to six study visits scheduled on three days over a period of approximately 2-3 weeks.

Each subject will be given a unique ID number. All subjects who sign a consent document will be included in the subject enrollment log which will include; subject ID, date of consent, date of screening, date of study completion, date of discontinuation (if required), reason for discontinuation (if required).

Additionally, all subjects must meet the study inclusion and exclusion criteria listed below.

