### 9.2.1 Contact lenses

All subjects will be trial fitted and, if suitable, dispensed the MyDay Sphere and the MyDay Energys lens brand. The study lenses will be provided by the Sponsor. Details of the contact lenses are shown in Table 1.

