**Figure 2: Flow chart for participants depending on habitual lens type.**

#### **Habitual MyDay Sphere wearers (Visit 1):**

Participants that habitually wear MyDay Sphere lenses will attend Visit 1 wearing their own MyDay Sphere lenses for **at least 2 hours** prior to the visit.

Data to be collected:

- Participant demographics, including Race and Ethnicity
- Habitual contact lens type and prescription
- Wearing times with habitual lenses:
  - Wearing time today (hours).
  - Average daily wearing time (hours/day)
  - Number of days/week (lenses are worn)
- Health and medication.

- [REDACTED]
- [REDACTED]
- Remove contact lens
- Automated refraction and keratometry
- [REDACTED]
- If at this point the subject is found to be ineligible, then complete an Exit form and exit the subject from the study.
- Eligibility will be confirmed and the participant continues right away with **Visit 2**

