### 9.3.2 Visit 2: Dispense MyDay Sphere

- Insert MyDay Sphere lenses (For habitual MyDay wearers, ensure to use updated power if an overrefraction was found)
  - [REDACTED]
  - [REDACTED]
- Fit assessment of MyDay Sphere
  - Centration: Optimum, decentration acceptable, decentration unacceptable
    - [REDACTED]
    - [REDACTED]
  - Post-blink lens movement, 0-4, 1 step, 0 = Insufficient, unacceptable movement
    - [REDACTED]
  - Overall fit acceptance 0-4, 0.5 step, 0 = Should not be worn
    - If overall fit acceptance  $\leq$  2, provide reason
- Provide sufficient MyDay Sphere to wear daily for at least 7 days
- After at least 7 days of MyDay Sphere, participant returns for Visit 3 wearing MyDay Sphere for at least 2 hours on that day
  - [REDACTED]

[figure not shown]

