### 9.3.3 Visit 3: Baseline MyDay Sphere review

Visit 3 occurs  $\geq$ 7 days after visit 2. The following procedures will be conducted during this visit to determine the baseline MyDay Sphere performance:

[figure not shown]
- Changes to health or medication

[figure not shown]
- Fit assessment of MyDay Sphere

[figure not shown]
- Centration: Optimum, decentration acceptable, decentration unacceptable

- Post-blink lens movement, 0-4, 1 step, 0 = Insufficient, unacceptable movement

[figure not shown]

- Overall fit acceptance 0-4, 0.5 step, 0 = Should not be worn

- If overall fit acceptance  $\leq 2$ , provide reason

- Remove contact lenses

- Participant continues right away with Visit 4

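### Does it matter that Table 2 makes Visit 2 conditional while section 9.3 sends every habitual MyDay Sphere wearer to it?

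*Combined protocol and SAP*

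**What the plan says.** Two places suggest that a habitual Sphere wearer with unchanged power does not need Visit 2.

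- Table 2 (section 9.3), note on Visit 2: "Visit 2 is only necessary if a change in MyDay Sphere lens power is required, or if a fit with MyDay Sphere is required". The note ties that fit to adaptation.
- Section 4: when acuity and power are already optimal, "the participant will continue to wear MyDay Sphere in the same prescription for at least 7 days". Dispensing for this period is described only for a changed power or for wearers of other lenses.

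Three places suggest that the same person does attend, or is at least fitted and given study lenses.

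- Section 9.3.1, under habitual MyDay Sphere wearers: "Eligibility will be confirmed and the participant continues right away with" Visit 2. No exception is visible.
- Section 9.3.2, at lens insertion: "For habitual MyDay wearers, ensure to use updated power if an overrefraction was found"; and later, "Provide sufficient MyDay Sphere to wear daily for at least 7 days".
- Section 9.2.1: "All subjects will be trial fitted and, if suitable, dispensed the MyDay Sphere and the MyDay Energys lens brand".

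Two further statements bear on the point indirectly. Section 9.1 says "Each subject will be required to attend up to six study visits". Section 9.3.3 sets Visit 3 at no less than "7 days after visit 2", whereas Table 2 counts it from V1.

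**The concern.** Visit 2 is the only visit before baseline at which the visible text has Sphere centration, movement and overall fit acceptance graded. These are the secondary and primary outcome variables. Section 11.1 plans paired tests over time as well as between lenses, names no visits, and drops missing data points without imputation.

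If the over-time test for Sphere ran from Visit 2 to Visit 3, its population would depend on which passage a site followed. On one reading it would include everyone. On the other it would leave out established Sphere wearers by design and describe only people newly fitted or given a new power. Sites might also differ on whether established wearers use their own or study-dispensed lenses before baseline. In addition, the Visit 3 window in section 9.3.3 would have no starting point for anyone who skipped Visit 2.

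**Working it through.** **Step 1: the plan's own figure.** Section 5.1 gives a difference of 0.16, an SD of at most 0.4, alpha 0.05, 73 participants and 92% power. I take the test as two-sided and the SD as that of paired differences; the section states neither.

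- Noncentrality = (0.16 / 0.4) × √73 = 0.4 × 8.544 = 3.418, with 72 degrees of freedom.
- Power from the noncentral t distribution = 92.1%, which reproduces the stated 92%.
- At the dispensing target of 80: noncentrality = 0.4 × 8.944 = 3.578 and power = 94.2%.
- Loss allowed between 80 and 73: 7 / 80 = 8.75%.

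None of these inputs refers to Visit 2.

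**Step 2: which grades each group has.** These are the visits at which each group's fit is graded, for participants who complete the study.

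| Group | Visit 2 by Table 2 note | Visit 2 by 9.3.1 and 9.3.2 | Visit 3 (Sphere) | Visit 5 (Energys) |
|---|---|---|---|---|
| Habitual Sphere, power unchanged | not needed | yes | yes | yes |
| Habitual Sphere, power changed | yes | yes | yes | yes |
| Other habitual lens | yes | yes | yes | yes |

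The readings differ in one cell. Section 9.3.3 makes Visit 3 the measure of baseline Sphere performance, and section 4 likewise places baseline after the Sphere wearing period. Visit 3 against Visit 5 is therefore the natural primary pair, and its count is the same on both readings.

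**Step 3: the timing anchor.** Table 2 lets Visit 2 coincide with Visit 1, and sections 9.1 and 9.3 fit all visits into three days. For anyone who attends Visit 2 on the first day, counting from Visit 1 or from Visit 2 gives the same date. For anyone who does not attend it, the Table 2 anchor still applies.

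**Step 4: can the effect on an over-time Sphere test be sized?** Let h be the share of participants who are habitual Sphere wearers with unchanged power. The protocol does not give h. With 80 participants, Visit 2 to Visit 3 pairs number 80 if all attend and 80 × (1 − h) if this group does not. For an assumed h of 25%, 50% or 75%, that is 60, 40 or 20 pairs. Power for these counts would not be informative. The 0.16 and 0.4 come from a comparison between two lenses in another product pair and say nothing about change within Sphere over a week.

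**The case for a change.** The strongest case for acting is that the contradiction is real, visible and cheap to remove. The Table 2 note and the routing line in section 9.3.1 cannot both describe the unchanged-power group. Reading the note as making Visit 2 optional only moves the decision to each site. The variables graded at Visit 2 are the trial's outcome variables, and section 11.1 leaves its over-time tests open.

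The inconsistency stands, but the rest carries less weight.

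- The direct conflict is narrow: the Table 2 note against section 9.3.1, with support from 9.3.2 and 9.2.1. Sections 4 and 9.2.1 do not name Visit 2. The maximum visit count in section 9.1 is compatible with either rule. The over-refraction remark in 9.3.2 could also cover a wearer whose power changes in one eye only.
- Section 9.3.1 refers to Figure 2 for routing by habitual lens type. That figure is not shown, and some Visit 1 steps are blacked out. A routing rule, or a Visit 1 fit grade, may lie there.
- A Visit 2 to Visit 3 Sphere test is an inference. Sections 2 and 3 concern Sphere against Energys. The over-time wording could equally mean Energys from dispensing to review.
- On lens source, both readings have the participant in MyDay Sphere at the established power, and section 9.2.8 already allows sponsor-supplied or locally sourced lenses. Nothing in the document suggests that the source alters a fit grade.

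**Conclusion.** This is a clerical inconsistency that leaves the analysis as it is. It affects one group at one visit, and the effect on the primary comparison, the sample size and the stated power is nil. That rests on the primary pair being Visit 3 against Visit 5. Section 11.1 does not name these visits, but sections 4, 9.3.3 and 9.3.5 support them.

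An analyst who chose to summarise Visit 2 Sphere grades would see from the case report forms who had one, and would report that number and describe the subset. No stated result or conclusion of the trial depends on such a summary. The passages on who attends Visit 2 must still be reconciled as an editorial matter. Which attendance rule is right is for the sponsor to say.

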### **9.3.1 Visit 1: Screening and establish optimum power of MyDay Sphere**

Participants will attend a screening visit during which the subject will be required to read and sign an informed consent for prior to enrolment. When the subject has signed the consent form, the subject will be considered to be enrolled in the study. The investigator should also sign the consent form. The subject will be provided with a copy of the consent and the original will be kept in the subject's paper chart. It may also be scanned into the subject's electronic medical record (EMR) file.

Participants will be assigned a study ID number when they sign the informed consent document, and before their eligibility for the study has been confirmed. Subjects must be enrolled sequentially. The subject enrollment log will be updated. Ineligible participants will be discontinued from the

study. Depending on the participant's habitual lens type, participants may follow the following procedures and visits outlined (illustrated in Figure 2).

**Figure 2: Flow chart for participants depending on habitual lens type.**

#### **Habitual MyDay Sphere wearers (Visit 1):**

Participants that habitually wear MyDay Sphere lenses will attend Visit 1 wearing their own MyDay Sphere lenses for **at least 2 hours** prior to the visit.

Data to be collected:

- Participant demographics, including Race and Ethnicity
- Habitual contact lens type and prescription
- Wearing times with habitual lenses:
  - Wearing time today (hours).
  - Average daily wearing time (hours/day)
  - Number of days/week (lenses are worn)
- Health and medication.

- [REDACTED]
- [REDACTED]
- Remove contact lens
- Automated refraction and keratometry
- [REDACTED]
- If at this point the subject is found to be ineligible, then complete an Exit form and exit the subject from the study.
- Eligibility will be confirmed and the participant continues right away with **Visit 2**

### **Habitual wearers of other lenses:**

Participants that habitually wear other soft lens types will be asked to attend Visit 1 wearing their glasses. Participant demographics, including their contact lens history, wear schedule, health and medication will be recorded. The following procedures will then be conducted:

- [REDACTED]
- [REDACTED]
- Eligibility will be confirmed and the participant continues right away with Visit 2

In some circumstances a repeated screening may need to be scheduled. Examples include, but are not limited to:

- Study procedures unable to be completed in time scheduled for visit;
- Study products not available at the time of the screening visit;
- A transient health condition which may affect the eye(s) (e.g. a common cold, active allergies, fatigue etc.);
- The short term use of medications (e.g. antibiotics, antihistamines etc.);
- Reassessment of baseline ocular conditions (e.g. corneal and/or conjunctival staining, scars etc.).

The maximum total number of screenings permitted per participant will be two.

### 9.3.2 Visit 2: Dispense MyDay Sphere

- Insert MyDay Sphere lenses (For habitual MyDay wearers, ensure to use updated power if an overrefraction was found)
  - [REDACTED]
  - [REDACTED]
- Fit assessment of MyDay Sphere
  - Centration: Optimum, decentration acceptable, decentration unacceptable
    - [REDACTED]
    - [REDACTED]
  - Post-blink lens movement, 0-4, 1 step, 0 = Insufficient, unacceptable movement
    - [REDACTED]
  - Overall fit acceptance 0-4, 0.5 step, 0 = Should not be worn
    - If overall fit acceptance  $\leq$  2, provide reason
- Provide sufficient MyDay Sphere to wear daily for at least 7 days
- After at least 7 days of MyDay Sphere, participant returns for Visit 3 wearing MyDay Sphere for at least 2 hours on that day
  - [REDACTED]

[figure not shown]
### 9.3.3 Visit 3: Baseline MyDay Sphere review

Visit 3 occurs  $\geq$ 7 days after visit 2. The following procedures will be conducted during this visit to determine the baseline MyDay Sphere performance:

[figure not shown]
- Changes to health or medication

[figure not shown]
- Fit assessment of MyDay Sphere

[figure not shown]
- Centration: Optimum, decentration acceptable, decentration unacceptable

- Post-blink lens movement, 0-4, 1 step, 0 = Insufficient, unacceptable movement

[figure not shown]

- Overall fit acceptance 0-4, 0.5 step, 0 = Should not be worn

- If overall fit acceptance  $\leq 2$ , provide reason

- Remove contact lenses

- Participant continues right away with Visit 4

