**Secondary outcomes:**

- Lens centration & lens movement (Appendix 9)

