### 5.1 Sample Size Calculation

A sample size calculation was made based on the primary outcome variable of lens fit acceptance grade, using data from a previous study: EX-MKTG-63. In this previous study the lenses compared were Biofinity and Biofinity Energys and for lens fit acceptance the difference between mean results

was 0.16, with a standard deviation of not greater than 0.4. For alpha 0.05, a sample size of 73 provides power of 92%. This variable will be graded using a 0-4 scale with 0.5 steps. Therefore, to allow for drop-outs and protocol deviations affecting inclusion in the analysis cohort, dispensing to 80 participants will be targeted.

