### **11.1 Statistical analysis**

---

Descriptive statistics will be provided on information regarding baseline variables (e.g., age, gender). Differences between lenses and over time will be compared using Paired t-tests. Paired t-tests /analysis of variance for normal (interval/continuous) data. The appropriate test will be selected based on tests of normality. Means and standard deviations will be provided for each variable.

All participants who were evaluated will be used in the analysis. In the event of missing data, individual data points will be excluded in the analysis and not extrapolated from the collected data.

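### If the best post-blink movement grade lies inside the 0-4 scale, the signed mean and paired test planned in section 11.1 do not measure movement quality (secondary outcome; minor, conditional on the Appendix 9 anchors)

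*Combined protocol and SAP*

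**What the plan says.** The secondary outcomes under section 2 are listed as "Lens centration & lens movement (Appendix 9"), so movement is a named outcome and its grading is defined in that appendix.

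Sections 9.3.3 (Sphere, Visit 3) and 9.3.5 (Energys, Visit 5) use the same item: "Post-blink lens movement, 0-4, 1 step, 0 = Insufficient, unacceptable movement". The same item is used when Sphere is dispensed (section 9.3.2). Only the zero anchor can be read in the public text. The anchors for grades 1 to 4 are not visible, and that is not a fault of the plan.

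The primary outcome sits next to it in section 9.3.3 with a different kind of zero: "Overall fit acceptance 0-4, 0.5 step, 0 = Should not be worn". That anchor states a judgement and names no direction of misfit.

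For analysis, section 11.1 says "Differences between lenses and over time will be compared using Paired t-tests" and "Means and standard deviations will be provided for each variable". The only visible rule for choosing the test is "The appropriate test will be selected based on tests of normality". Section 11.1 gives movement no rule of its own.

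**The concern.** The movement zero says which way the lens fails (too little movement) as well as that it fails. A scale that starts at too little may pass through an optimum and end at too much. On such a scale a higher grade is better below the optimum and worse above it, so the signed difference between lenses has no fixed meaning as better or worse.

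Two consequences would follow. A lens that gives both more tight and more loose fits than the control could show little or no mean difference. And a non-zero mean difference would show that movement changed, but not which lens moves better. The aim in section 2 is to learn whether wearers can be refitted successfully, so the second gap matters even when nothing cancels.

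This is a different matter from centration, which is categorical. Movement is numeric and ordered, but its direction of benefit may reverse within the scale.

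**Working it through.** **The plan's own figure.** The only sample-size figure concerns overall fit acceptance. Section 5.1 gives a mean difference that "was 0.16, with a standard deviation of not greater than 0.4", and states "For alpha 0.05, a sample size of 73 provides power of 92" per cent. Treating 0.4 as the SD of paired differences, the noncentrality is (0.16/0.4) × √73 = 3.418 with 72 degrees of freedom. A two-sided paired t-test at 0.05 then has power 92.1%. The figure reproduces, and it does not involve movement.

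**Inputs for movement.**
- Scale 0 to 4 in whole steps; zero means insufficient movement (sections 9.3.3 and 9.3.5).
- Planned statistics: mean, SD and signed paired difference (section 11.1).
- Location of the optimum: not visible. Assumed to be grade 2, with 3 and 4 as the range.
- Grade distributions: constructed for illustration, not forecasts.

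**Same score, opposite meaning (optimum 2).**
- 1 to 2: signed change +1; distance from optimum falls from 1 to 0 (better).
- 3 to 4: signed change +1; distance rises from 1 to 2 (worse).

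**Example A: balanced shift to the extremes.** All Sphere grades are 2. Energys grades are 10% at 0, 80% at 2 and 10% at 4.
- Energys mean = 0.1×0 + 0.8×2 + 0.1×4 = 2.0, so the paired difference is 0.
- Share at an extreme = 0.1 + 0.1 = 20%, against 0% with Sphere.
- Energys SD = √(0.2 × 2²) = √0.8 = 0.89, against 0 with Sphere.
- With 5% + 5% at the extremes, SD = √0.4 = 0.63. With 20% + 20%, SD = √1.6 = 1.26. The mean difference stays at 0.

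**Example B: balanced one-grade shift, n = 80.** All Sphere grades are 2. Energys has 10 at grade 1, 60 at 2 and 10 at 3.
- Signed difference = (−10 + 10)/80 = 0.00; paired t-test p = 1.0.
- Distance from optimum rises by 20/80 = 0.25 (paired t-test p ≈ 2×10⁻⁶).
- Share at the optimum falls from 100% to 60/80 = 75%.
- Energys SD = 0.50, against 0.
- A signed-rank test, should a failed normality check lead to one, would not help. The 20 non-zero differences tie at an average rank of 10.5, so each side sums to 10 × 10.5 = 105 and the test sees no difference.

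**Example C: unbalanced shift, n = 80.** All Sphere grades are 2. Energys has 15 at grade 1, 60 at 2 and 5 at 3.
- Signed difference = (−15 + 5)/80 = −0.125.
- Distance from optimum rises by 20/80 = 0.25.
- The signed result is half the size of the loss, so the effect is diluted, not erased.

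**Range for the optimum.** Of 80 participants, 20 move one grade down and 20 one grade up where the scale allows.

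| Assumed optimum | Signed difference | Mean distance from optimum |
|---|---|---|
| 2 | 0.00 | 0.50 |
| 3 | 0.00 | 0.50 |
| 4 | −20/80 = −0.25 | 0.25 |

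With an optimum of 4 nothing can move above it, the two measures agree in size, and there is no cancellation.

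**The case against.** The strongest objection is that the condition cannot be confirmed. Only the zero anchor can be read. A directional word at zero makes an interior optimum plausible, particularly beside the non-directional zero for overall fit, but it does not locate the optimum. The text hidden beneath the movement item might also record direction or acceptability. This stands, and it is why the point is conditional.

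Second, the examples are constructed. Section 9.1 requires an acceptable fit for inclusion, and section 9.2.1 dispenses lenses only if suitable. The two lenses share material, base curve and diameter (Table 1). Extreme grades are therefore less likely than in Example A, and exact balance is a special case. This also stands. Example B avoids extreme grades, and Example C shows that partial balance still dilutes.

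Third, the planned SD would reveal extra spread (0.89 in Example A and 0.50 in Example B, each against 0). That is correct, but no comparison of spread is planned, and an SD does not say whether lenses became tighter or looser.

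Fourth, the signed difference is a legitimate answer to whether movement changed, and a shift in one direction would appear in it. That is right, and it is a reason to keep it as a description.

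A reader might go further and infer that the movement outcome can say nothing about the refit, or that the study's main conclusion is at risk. The documents support neither. One-directional shifts remain visible. The hypotheses and the sample size rest on overall fit acceptance. Its zero names no direction, so a lens judged unwearable because it is too tight or too loose should lower that grade either way.

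**Conclusion.** The point holds in conditional form and is minor. If Appendix 9 places the best movement grade inside the scale, the signed mean and paired test do not measure movement quality. Opposite changes can carry the same sign, and shifts to tighter and looser fits offset each other: fully when balanced (difference 0 with 20% at the extremes in Example A) and partly otherwise (half the loss in Example C). If grade 4 is best, the scale runs one way and the point falls away.

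The conclusion rests on one assumption, an interior optimum. The directional zero suggests this but does not establish it. The effect is confined to a secondary outcome. The primary outcome, the hypotheses and the 92% power figure are untouched.

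**What to change.** Check the anchors in Appendix 9. If grade 4 is the best movement grade, one clarifying phrase in section 11.1 closes the point.

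If the optimum is interior, add the following to section 11.1:

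1. Report the full movement grade distribution for each lens at Visit 3 (Sphere) and Visit 5 (Energys), with counts of insufficient and excessive movement.
2. Compare the within-participant proportion with optimal or acceptable movement between those visits by McNemar's test. Fix the cut from Appendix 9 in advance, because it matters. In Example B, counting only grade 2 as a success gives 20 discordant pairs, all in one direction (exact two-sided p = 2 × 0.5²⁰ ≈ 2×10⁻⁶). If grades 1 and 3 also count as acceptable, there are none. If both eyes are graded, reduce them to one result per participant first.
3. The distance from the optimal grade may be used as a supportive score. It should not stand alone, because it treats too tight and too loose as equally bad and drops direction.
4. Keep the raw mean and paired difference only as a description of the direction of change.

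The cost is a few table rows and one derived variable. No new data, visits or participants are needed.
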